8.9 Immunogenicity Assessments

Not applicable

8.10 Health Economics

Not applicable

9 Statistical Considerations

Analysis of all data, including safety and PK data will be performed by the Sponsor or its designee. The results of all study parts will be reported in the CSR. Details of the analysis of safety, efficacy, PK, Pd, and biomarker data will be presented in the iAP.

9.1 Statistical Hypotheses

No formal hypothesis testing will be performed. This is an exploratory study.

9.2 Sample Size Determination

Part 1A – Dose Escalation

A Bayesian 2-parameter Logistic Regression Model will assist the SMC in dose recommendations. The planned cohort size is approximately 3 participants. The total sample size will depend on the number of cohorts to be evaluated. Approximately 40 participants are planned to be assigned to study intervention, including 22 to 28 participants in Part 1A (planned 4 potential DLs of 100, 200, 400, and 600 mg), and 12 participants in Part 1B; the sample size for the MTD and/or RDE DL needs to be at least 6 participants.

Part 1B – Preliminary Food Effect Assessment Sample Size Justification

For a preliminary assessment of the effect of food on the systemic exposure of M4076, 12 participants will be randomized 1:1 in a randomized, 2-sequence, 2-period, cross-over design to receive a single dose M4076 under a fed condition in 1 of the following sequences 1) fasted followed by fed, or 2) fed followed by fasted. The dose of M4076 will be the RDE from Part 1A.

This sample size is expected to result in sufficient precision for the estimate of the ratio between PK parameters under fed and fasted conditions in order to guide further development. Assuming that the within-subject coefficient of variation (CV) for AUC_{0-24h} and C_{max} is between 10% and 30%, the 2-sided 90% confidence interval (CI) for the geometric mean ratio (GMR) will be contained in the boundaries presented in [Table 14](#), with 80% probability.

For example, if the within-subject CV is 20%, and a GMR of 50% is observed, then the 90% CI for the GMR will be contained in [35.6%; 70.2%] with 80% probability. With a CV of 30% and an observed GMR of 100%, the corresponding boundaries are [60.5%; 165%].

Table 14 80% Coverage Interval for the 90% Confidence Intervals for Estimated Fed/Fasted Ratio, n = 6 per Sequence (12 in total)

CV	GMR	80% Coverage Interval n = 6 per Sequence		
		Fed versus Fasted	Lower Bound	Upper Bound
10%	0.50		42.1%	59.3%
20%	0.50		35.6%	70.2%
30%	0.50		30.2%	82.7%
10%	1.00		84.3%	119%
20%	1.00		71.2%	140%
30%	1.00		60.5%	165%
10%	2.00		169%	237%
20%	2.00		142%	281%
30%	2.00		121%	331%

CV = coefficient of variation; GMR= Geometric mean ratio.

These calculations were performed using the module MTC1 1 of the software nQuery Advisor® 7.0 for natural logarithm transformed data, and back-transformed to the original scale.

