4.3 Scientific Rationale for Study Design

The Phase 1, dose-escalation study is designed to establish a safe and tolerable dose of M4076 monotherapy (Part 1A) and to investigate PK, Pd, and early signs of efficacy in participants with advanced solid tumors for which no standard therapy is available.

Rationale for the cross over design for the preliminary food effect assessment (Part 1B): The 2-sequence cross over design, as compared to an alternative parallel design, minimizes the number of study participants required to identify the effect of food on the PK of M4076 since each participant serves as their own control. The selected washout period will sufficiently remove M4076 from the systemic circulation to eliminate the risk of carryover effects which can be deleterious to the study's outcome and interpretation.

Participant involvement in development of the study design was not sought.

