### 16.1.3 Statistical Analysis of PK Parameter Data

Dose proportionality will be provided separately for  $AUC_{0-\infty}$ ,  $AUC_\tau$ ,  $AUC_{0-tlast}$  and  $C_{max}$  on study day 1 and 8 for Part 1A using a power model. The power model will have the form:

$$Y = a * (dose)^b$$

where Y is the PK parameter, and a and b are the coefficient and exponent, respectively, of the power equation. By taking the natural logarithm (ln), the power model can be analysed using linear regression and has the form:

$$\ln(Y) = \ln(a) + b * \ln(dose) + \text{error}$$

$$= \alpha + \beta * \ln(dose) + \text{error},$$

where  $\alpha$  is the intercept, and  $\beta$  is the slope, and  $\ln(dose)$  is based on the dose size for each subject. For each PK parameter, the point estimate of slope  $\beta$  and its 95% CI will be provided. In addition, the estimated regression line will be overlaid on the individual points in the corresponding scatter plot (log-log scale).

Dose proportionality will be declared if the 90% confidence interval (CI) for  $\beta$  is entirely contained within the critical region,

$$\left( 1 + \frac{\ln(0.50)}{\ln(r)}, 1 + \frac{\ln(2.00)}{\ln(r)} \right)$$

where  $r$  is the ratio of the highest and the lowest dose in a given part of the study. Dose proportionality for participants who were administered the study intervention will be tested for  $C_{max}$  and  $AUC_{0-\infty}$ ,  $AUC_\tau$ ,  $AUC_{0-tlast}$  on Day 1 and at steady state.

Since the study is neither optimally designed nor powered to confirm the presence or absence of meaningful departures from dose proportionality, these results should be interpreted with caution. In addition, graphical assessment would also be considered to understand dose proportionality.

If the samples remain above LLOQ for the whole dosing interval, then  $AUC_{0-t_{last}}$  will be the same as  $AUC_{\tau}$  for Part 1A as there is another dose after 24 hours

A statistical analysis will be conducted to investigate the food effect on the treatment by comparing (fed) treatment to (fasted) treatment for Part 1B.

The natural log (ln)-transformed  $AUC_{0-\infty}$ ,  $AUC_{\tau}$ ,  $AUC_{0-t_{last}}$  and  $C_{max}$  will be analyzed using a mixed effect model. The model will include planned treatment sequence, period, and actual treatment as fixed effects, and subject within planned treatment sequence as a random effect.

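### Table 14 states food-effect confidence limits that are twice as wide on the log scale as the 12-participant crossover gives, in all nine rows

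*Protocol*

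**What the plan says.** Protocol Section 9.2 sets the Part 1B design: "12 participants will be randomized 1:1 in a randomized, 2-sequence, 2-period, cross-over design". The variability input is a within-subject figure: "Assuming that the within-subject coefficient of variation (CV) for AUC_{0-24h} and C_{max} is between 10% and 30" percent. The precision claim is that "the 2-sided 90% confidence interval (CI) for the geometric mean ratio (GMR) will be contained in the boundaries" of Table 14 with 80% probability. The table's title is "80% Coverage Interval for the 90% Confidence Intervals for Estimated Fed/Fasted Ratio, n = 6 per Sequence (12 in total").

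Two examples follow in the text. For a CV of 20% and an observed ratio of 50%, "then the 90% CI for the GMR will be contained in [35.6%; 70.2%] with 80% probability". The other is "With a CV of 30% and an observed GMR of 100%, the corresponding boundaries are [60.5%; 165" (percent). A note under the table says that the limits were computed with an nQuery Advisor module on natural-log data and transformed back.

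Protocol Section 4.3 chooses the crossover "since each participant serves as their own control". The planned analysis agrees with that choice. Protocol Table 19 specifies a mixed model with intervention, period and sequence, and SAP Section 16.1.3 fits the same structure with "subject within planned treatment sequence as a random effect" and reports 90% confidence intervals.

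**The concern.** The printed limits look too wide for a crossover. At a within-subject CV of 30%, 12 people who each supply a fed and a fasted profile should not need limits of 60.5% to 165% around a ratio of 100%. A constant excess in every row would point to a formula or input error and not to a deliberate margin.

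The stake is the sample-size argument. Table 14 and its two examples are the only figures behind the statement that 12 participants give adequate precision. If they are wrong, the document describes a design much less precise than the one that will be run. The number of patients who undergo two intensive PK profiles and, unless contraindicated, paired biopsies then rests on a calculation for a different estimator.

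**Working it through.** **Inputs, all from Protocol Section 9.2.** Two sequences of n = 6, so 10 error degrees of freedom. Within-subject CV of 10%, 20% or 30%. Two-sided 90% interval. 80% probability, conditional on the observed ratio. Natural-log scale.

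- Log-scale within-subject SD: σ_w = √ln(1 + CV²) = 0.0998, 0.1980, 0.2936.
- t(0.95, 10) = 1.812.
- 80% coverage factor: √(χ²(0.80, 10)/10) = √(13.442/10) = 1.159.

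**Standard error of the treatment effect.** Each participant's period difference has variance 2σ_w². The difference between the two sequence means of these has variance 2σ_w² × (1/6 + 1/6) = 0.667σ_w², so its standard error is 0.816σ_w. That contrast estimates twice the fed/fasted effect. The effect is half of it, with standard error 0.408σ_w, which equals σ_w√(2/12).

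**Reproducing the plan's figures.** Without the halving, the half-width is 1.812 × 0.816σ_w × 1.159 = 1.716σ_w, or 0.171, 0.340 and 0.504 for the three CVs. Back-transformed:

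| CV | Ratio | Un-halved formula | Table 14 |
|---|---|---|---|
| 20% | 0.50 | 35.6–70.2% | 35.6–70.2% |
| 30% | 0.50 | 30.2–82.7% | 30.2–82.7% |
| 10% | 1.00 | 84.3–118.7% | 84.3–119% |
| 20% | 1.00 | 71.2–140.5% | 71.2–140% |
| 30% | 1.00 | 60.4–165.5% | 60.5–165% |
| 30% | 2.00 | 120.9–331.0% | 121–331% |

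All nine rows match to rounding, apart from one last-digit difference (60.4 against 60.5).

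**Correct figures.** With the halving, the half-width is 1.812 × 0.408σ_w × 1.159 = 0.858σ_w, or 0.0856, 0.170 and 0.252:

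| CV | Ratio 0.50 | Ratio 1.00 | Ratio 2.00 |
|---|---|---|---|
| 10% | 45.9–54.5% | 91.8–108.9% | 183.6–217.9% |
| 20% | 42.2–59.3% | 84.4–118.5% | 168.8–237.0% |
| 30% | 38.9–64.3% | 77.7–128.6% | 155.5–257.3% |

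Across the 18 printed limits, the log half-width is 1.97 to 2.03 times the correct one. The three-digit rounding explains the spread.

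**Simulation.** In 200,000 simulated 2x2 crossovers, the 80th percentile of the half-width was 0.170 at a CV of 20% and 0.252 at 30%.

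**Probability actually attached to the printed limits.** The interval lies inside limits twice as wide when χ² on 10 df is at most 4 × 13.442 = 53.77. The chance of exceeding that is about 5 in 100 million, so the stated 80% is really above 99.9999%.

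**Other readings tried.** Multipliers of σ_w, against the 1.716 needed:

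- paired analysis on 11 df: 0.846
- 95% interval: 1.055
- 99% interval: 1.500
- 95% coverage: 1.001
- 6 participants in total: 1.405 (paired) or 1.506 (crossover)
- two parallel groups of 6 with SD σ_w: 1.213
- containment around the true ratio rather than the observed one: 1.286 for the crossover, 1.818 for two groups of 6

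None reproduces the table. As labelled, it would be right only for within-subject CVs of about 20%, 41% and 64%.

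**Scale of the error.** Six participants in total (3 per sequence, 4 df) would already give limits inside every printed row. At a ratio of 1.00 these are 86.1–116.2%, 74.2–134.8% and 64.3–155.6%.

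**The case against.** The best defence is that the error does no harm to the trial. It is conservative: 12 participants give better precision than claimed, so the statement that the cohort is large enough survives and is strengthened. Part 1B is optional and preliminary, food effect is a secondary objective, and Protocol Section 9.1 rules out formal testing. Table 14 does not enter the analysis, since SAP Section 16.1.3 computes the interval from the data. Neither document sets a no-effect limit for food, so no decision rule turns on the printed widths. All of this stands. It limits the consequence but does not make the figures right.

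Two further points also stand. The software run is not visible, so the missing division by 2 is the probable cause and not a proven one. The corrected limits also assume 12 evaluable participants. SAP Sections 16.1.4 and 16.1.5.1 allow profiles, and AUC extrapolated to infinity in particular, to be left out of the statistical evaluation. At a CV of 30% and a ratio of 1.00, the limits widen to 75.1–133.2% with 10 evaluable (5 per sequence) and to 71.1–140.6% with 8 (4 per sequence). Even those are well inside the printed 60.5–165%.

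**Conclusion.** The concern holds. All nine rows of Table 14 and both worked examples are too wide by a factor of 2 on the log scale, and the 80% probability attached to them is wrong. The conclusion uses only inputs stated in Section 9.2 and the standard crossover estimate that both documents plan to use. It assumes 6 evaluable participants per sequence and log-normal within-subject variation. It does not depend on how the error arose. The direction is conservative, so neither the sample size nor the analysis is undermined. What fails is the stated precision, which is the only quantitative justification given for 12 participants.

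**What to change.** Check the input to the nQuery module, in particular which SD was entered and whether the sequence contrast was halved. Then replace the nine rows of Table 14 with the corrected limits in the working above. Change the two examples in the text to 42.2–59.3% (CV 20%, observed ratio 50%) and 77.7–128.6% (CV 30%, observed ratio 100%). Keep 12 participants and rest the precision statement on the new figures. Add a sentence that they assume 12 evaluable participants, with the limits for 10 and 8 alongside. The cost is protocol wording at the next amendment. No change to design, conduct, analysis or number of participants is needed.

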9.3 Populations for Analyses

The analysis populations are specified below (Table 15). The final decision to exclude participants from any analysis population will be made during a data review meeting prior to database lock. However, for the DLT analysis set, the decision on evaluability will be made by the SMC.

Table 15 Populations for Analyses

Analysis Set	Description
Screening (SCR)	All participants, who provided informed consent.
Full Analysis Set (FAS) / Safety Analysis Set (SAF)	All SCR participants, who received at least one dose of any study intervention. Analyses will consider participants as treated.
DLT	All FAS/SAF participants who meet at least one of the following criteria: 
Experienced at least one DLT during the DLT period, regardless of the administered number of doses of study intervention/completion of the DLT period.Received at least 80% of the planned cumulative dose during the DLT period of each study intervention and completed the DLT period.Additionally, participants who did not receive 80% of the planned total dose of study intervention, but at least 80% dosing of a different dose cohort and finished the DLT period are eligible for the DLT analysis set to be analyzed in the highest dose cohort for which they received 80% of dosing. The final decision on evaluability for dose escalation analysis will be made by the SMC (e.g. considering relevant deviations from dosing schedule).
PK (PKAS)	All participants who receive at least one dose of study intervention and provide at least one measurable post-dose concentration. A measurement below lower limit of quantification (BLQ) is considered a valid measurement. Participants will be analyzed according to the actual treatment they received. All PK analyses will be based on the PK Analysis Population.
Pd	All participants, who receive at least one dose of study intervention, have no clinically important protocol deviations or important events affecting Pd, and provide at least one measurable Pd endpoint postdose. Participants will be analyzed per the actual study intervention they received. All Pd analyses will be based on this analysis population.

DLT = dose limiting toxicity; Pd = pharmacodynamics; PK = pharmacokinetics; PKAS = pharmacokinetic analysis set.

9.4 Statistical Analyses

All analyses will be prepared by DL and will be described in detail in the iAP. Except for the analysis of DLTs, all analyses will be performed on the Safety Analysis population.

The following statistics will be used to summarize the study data (e.g. baseline characteristics) unless otherwise specified:

- **Continuous variables:** number of non-missing observations, mean, standard deviation, median, 25% Percentile to 75% Percentile (Q1 to Q3), minimum, and maximum, 95% CIs for the mean, as appropriate.

- **Categorical variables:** frequencies and percentages.

The calculation of proportions will be based on the number of participants in the analysis set of interest, unless otherwise specified in the study iAP.

Baseline is defined as last non-missing value prior to first administration of study intervention

On-treatment values are defined as those measured during the study intervention period.

Besides the details outlined below, more details will be specified in the iAP finalized before database lock.

9.4.1 Efficacy Analyses

All efficacy analyses will be performed on the Full Analysis Set population unless otherwise specified (Table 16).

Table 16 Part 1A Efficacy Analyses

Endpoint	Statistical Analysis Methods
Part 1A	
Primary	No primary efficacy endpoint is specified.
Secondary	
Objective response according to RECIST 1.1 assessed by Investigator	
ORR will be determined as the proportion of participants with a confirmed objective response of PR or CR. Confirmation of the response according to RECIST 1.1 will be required no sooner than 4 weeks after the initial documentation of CR or PR.
 
The number and proportion of overall response (defined as CR + PR) will be tabulated.
 
The 95% CI for the ORR will be calculated using the Clopper-Pearson method.

DoR according to RECIST 1.1 assessed by Investigator	
DoR is defined as the time (months) from first documentation of objective response (CR or PR) to the date of first documentation of PD or death due to any cause, whichever occurs first.
 
Duration of response data will be censored on the date of the last non-missing tumor assessment for participants who do not have an event (PD or death) or for participants for which the event is reported after two or more missed subsequent scheduled tumor assessments.
 
Participants who do not have a baseline tumor assessment or who do not have any post baseline tumor assessments will be censored at the date of the start of study intervention.
 
Kaplan-Meier estimates (product-limit estimates) will be presented for the analysis of DoR together with a summary of associated statistics (median DoR and response rate estimates at 3, 6, 12 months and every 6 months thereafter if applicable) including the corresponding 2-sided 95% CIs.

PFS according to RECIST 1.1 assessed by Investigator	PFS is defined as the time (in months) from date of first administration of study intervention to the date of the first documentation of PD or death due to any cause, whichever occurs first. The censoring rules for PFS are as described above for DoR. Kaplan-Meier estimates (product-limit estimates) will be presented for the analysis of PFS together with a summary of associated statistics (median PFS time and PFS rate estimates at 3, 6, 12 months and every 6 months thereafter if applicable) including the corresponding 2-sided 95% CIs.
Tertiary/Exploratory	Will be specified in the Integrated Analysis Plan, finalized before database lock.

CI = confidence interval; CR = complete response; DoR = duration of response; ORR = objective response rate; PD = disease progression; PFS = progression-free survival; PR = partial response; RECIST = Response Evaluation Criteria in Solid Tumors.

9.4.2 Safety Analyses

The DLT analysis will be performed on the DLT Analysis population. All other safety analyses will be performed on the Safety Analysis population. See [Table 17](#).

Table 17 Safety Analyses

Endpoint	Statistical Analysis Methods
Part 1A	
Primary	
DLT	
AEs classified as DLTs as assessed by SMC will be evaluated.
 
Bayesian dose toxicity analysis.
 
At primary analysis for Part 1A, the number and proportion of participants experiencing DLTs will be reported by dose level, based on observations during the first study intervention evaluation (21 days). Posterior probabilities (2.5%, 25%, 50%, 75%, and 97.5% quantiles) for DLT rates at selected doses will be estimated from the Bayesian dose toxicity model.
 
Sensitivity analysis using frequentist modeling (without prior).
 
Regarding intercurrent events: These are considered in the definition of DLTs and DLT analysis set.

Secondary	
AE	
AEs will be coded according to the latest available version of MedDRA. Severity of AEs will be graded using the NCI-CTCAE (Version 5.0). Missing classifications concerning study intervention relationships will be considered related to the study intervention. TEAEs are defined as AEs emerging or worsening after start of study intervention until 30 days after the end of study intervention period.
 
Following TEAEs will be presented in summaries by incidence and type according to MedDRA System Organ Classes and Preferred Terms:
 
 • TEAEs. • SAEs. • TEAEs related to study interventions. • NCI-CTCAE Grade 3 or higher TEAEs. • NCI-CTCAE Grade 3 or higher related TEAEs. • TEAEs leading to interruptions, dose modifications of study interventions. • TEAEs leading to permanent discontinuation of study interventions. • TEAEs leading to death.

Death	Counts and percentages.
Changes in laboratory measurements	Summary statistics and boxplots. Laboratory results will also be classified by Grade according to NCI-CTCAE. Worst on-treatment grades as well as shifts to worst on treatment grades will be summarized. Measurements without NCI-CTCAE grading will be summarized by above, within and below normal limits.
Vital signs and ECOG performance status	Baseline and on-treatment values will be summarized. Summary statistics: Increase/decrease in vital signs (body temperature, heart rate, blood pressure and respiratory rate), ECOG performance status and body weight will be categorized and summarized descriptively in shift tables from baseline to minimum and maximum on-treatment values.
ECGs	Clinically significant, abnormal findings from 12-lead ECGs during the treatment phase will be presented descriptively. Change from baseline to worst on-treatment value will be summarized descriptively for the QTcF interval in accordance to ICH E14 criteria.
CCI	

AE = adverse event; DLT = dose limiting toxicity; ECG = electrocardiogram; ECOG = Eastern Cooperative Oncology Group; ICH = International Council for Harmonisation; MedDRA = Medical Dictionary for Regulatory Activities; NCI-CTCAE = National Cancer Institute Common Terminology Criteria for Adverse Events; QTcF = QT interval corrected using Fridericia's formula; SAE = serious adverse event; SMC = safety monitoring committee; TEAE = treatment emergent adverse event.

9.4.2.1 Part 1A: Dose Escalation

Analyses to decide on dose escalation will be performed on the DLT set and will be based on available safety and preliminary PK data. To support the decision on dose escalation, the SMC will receive results of a Bayesian dose-toxicity model, including the recommendation of next DL. This Bayesian dose-toxicity model ([Neuenschwander 2008](#)) is further specified in [Appendix 12](#). For each SMC meeting, the model will be updated with the number of DLTs and evaluable participants per DL.

Potential DLs are: 100 mg (starting dose), 200 mg, 400 mg, 600 mg. However, the SMC may decide to have different, or additional DLs or skip DLs (total daily dose increases must not exceed 100% of the highest total daily DL currently considered safe). Based on the observed toxicity profile and available PK and Pd, DL(s) that are different to, or higher or lower than the prespecified DLs may be tested.

The dose suggested by the model for the next cohort will be based on [minimizing the Bayesian Risk](#).

The SMC may choose a different dose than suggested by the Bayesian escalation approach. Also, the SMC may decide to change the dosing regimen. In such a case the dose-toxicity model will be extended, or a separate model will be set up using the information from previous cohorts to define a new prior information for the new schedule.

The MTD will be defined by the SMC. The target DLT probability for the MTD is 30%.

Usually, decisions on dose escalation are taken once all participants of the most recent cohort have completed the DLT period or dropped out. In exceptional cases, however, the SMC may decide on the next cohort earlier, i.e., before the last participant of a cohort has finished the DLT

period (considering the model recommendation). Per definition of the DLT analysis set, participants who have not completed the DLT period are not included for update of the model, unless they experienced a DLT. However, data of such participants will be included at next SMC.

Details on analyses for SMC will be described in the SMC iAP.

[figure not shown]
Before first dosing, the assumed relationship between DL and toxicity is specified through the prior distribution. The prior distribution chosen for this study corresponds to the following (Table 18):

CCI

██████████	████	████	████	████	████
████	████	████	████	████	████
████	████	████	████	████	████

DLT = Dose limiting toxicity.

In Figure 3 several examples of dose escalation recommendations by the model for the first 3 cohorts (each with 3 participants) depending on the number of experienced DLTs (from 0 to 3) are shown:

Figure 3 Escalation Tree: Examples of Dose Recommendations Based on the Bayesian Model for the First 3 Cohorts

The recommendations illustrated in the decision tree are not binding. The SMC may choose a different dose than suggested by the Bayesian escalation approach.

Details of the model, including the prior distribution are in [Appendix 12](#).

